7.12. Stakeholder engagement

In order to gain insight into the perspectives of key stakeholder groups (e.g. Directors of Public Health, Community, Retail) we hold a 'Fresh Street' symposium. We will invite key stakeholders in public health nutrition, food insecurity and health inequalities from both government and third sector organisations. This will include representatives from the Healthy Start programme, national healthy eating awareness programmes (EatWell, Start4Life, Change4Life), the DWP Family Resources Annual Survey and also national dietary surveillance programmes. Symposium attendees will share what is known about place-based food subsidy approaches to public health nutrition and we will share our plans for assessing the impact of the Fresh Street intervention. This symposium will enable us to refine our plans, and in the longer term, help ensure that our study provides the evidence required by stakeholders on the impact of the intervention on the broad range of interconnected challenges for UK public health nutrition

7.13. Data management

The Fresh Street pilot study will collect data from a variety of sources (see Section 7.9 Data collection).

The PCTU Data Management team will provide advice and support to ensure data is collected, stored and managed safely and robustly for the pilot, including drafting the Data Management Plan, and assisting with data transfer and data storage.

Survey data will be collected initially in paper format, and if necessary, identical questions will be collected online using the SmartSurvey platform via our CitizenLab public engagement platform 'Healthy People, Healthy Places'. The SmartSurvey online platform is DSPT compliant with all data stored in the UK in an ISO27001 compliant data centre.

Responses to paper surveys will be retrospectively added to the online dataset via SmartSurvey.

Paper surveys will be drafted by the Fresh Street research team (CR, DU, GB) and reviewed and signed off by the statistical and data management teams. The development of online surveys on SmartSurvey will be completed by the Fresh Street research team following PCTU Data Management SOPs and processes. Any changes to the survey questions will be agreed by those who will be analysing the quantitative data (statisticians) and qualitative data (Fresh Street team).

Data storage

The PCTU Data Management team will advise on appropriate data storage strategies including integrated data validation checks and audit trails.

All electronic data for the Fresh Street pilot will be stored on the QMUL BCC Safe Haven environment (https://safehaven.bcc.qmul.ac.uk/). SmartSurvey data will be downloaded and stored in the secure QMUL BCC Safe Haven environment. PCTU based research team members will have assigned access rights to access and analysis the data.

The Data Management team will advise on the transfer, storage, back-up and archiving of data on the QMUL BCC Safe Have environment.

All paper records (completed paper surveys, consent forms and recruitment logs) will be held in designated locked cabinets. Only named, designated staff who have data protection training will be given access to the paper records held at QMUL and at the local research sites.

All mobile devices and media used to collect and transfer data will be encrypted.

Data access

The QMUL Fresh Street research team will have access to all pilot data. The data analysis team will remain blind to allocation.

Access to SmartSurvey data will be controlled using designated users with permitted access rights.

Local site teams (Doncaster, Bradford and Tower Hamlets) will have access to any data collected by their community researchers i.e. **household voucher data** and the **paper survey** and **qualitative data**.

Maintaining data security

The PCTU will advise on current regulatory framework regarding data protection and data management procedures in compliance with GDPR, the Data Protection Act and trial management regulations. This advice will apply to all data in the pilot trial. We will store the data for five years in line with the QMUL Records Retention Schedule. Data will be made available for re-use by other bona fide researchers.

7.14. Data analysis

Analysis of voucher distribution and redemption data will enable us to assess uptake of the intervention (objective b) including weekly spending patterns of each household - how many vouchers were spent, and when and where.

We will assess what proportion of households contacted provide valid baseline primary outcome measure responses (objective e).

Any analysis of outcome data will be by intention-to-treat. All clusters and households for whom an outcome is available will be analysed according to the group to which they were randomised. Households which cannot be linked to a street participating in the study will be excluded.

The primary outcome analysis will compare the mean difference between intervention and control in portions of FV eaten the day before. A mixed regression model will be used where an individual household outcome at follow-up is adjusted for baseline cluster (street) mean score and site, and within cluster correlation is allowed for.

There is likely to be some contamination relating to sharing of vouchers, sharing of information, supplier effects and household churn i.e. households moving into or out of the intervention/ control streets. Potential sources of contamination will be monitored throughout during qualitative interviews and analyses adjusted where possible.

7.15. Health economic evaluation

In the main trial, we will use prospectively collected study data to assess the cost of implementing and managing Fresh Street from the local public services' perspective, and the impact on FV consumption and diet quality, and using external data on the association between diet and mortality, the intervention's long-term impact on survival and quality of life. A further scenario analysis will include the likely impact of Fresh Street on household's private costs for FV. We will follow a bottom-up approach to estimate the resources used in the intervention, which include the vouchers' monetary value; resources for printing and delivery; promotional activities; vouchers' reimbursement to FV retailers; and general scheme management costs.

During the pilot trial we will consolidate our approach to assessing intervention's cost and assess the feasibility (i.e. response rates) of collecting self-reported healthcare utilisation data from participating households and FV prices' data (with focus on key high-demand FV products) from participating FV retailers.

7.16. Process Evaluation

Alongside the pilot trial, we will conduct a process evaluation to assist our interpretation of findings, and inform any future implementation of the Fresh Street intervention (objective f). This will help us refine our methods for the process evaluation that will run alongside the future main trial (objective g).

The process evaluation is informed by the Medical Research Council (MRC) guidance on evaluating complex interventions (Moore et al., 2015; MRC, 2008).

The process evaluation will aim to understand how the intervention was experienced by those delivering it (FV vendors, public health teams, local stakeholders) and receiving it (householders). The evaluation will provide insight into a) the process of implementing the intervention, b) the mechanisms of action of the intervention, and c) contextual factors which impact on intervention success. If the trial is positive, this will inform the implementation of the intervention and our theory of change/ logic model. If the trial is negative, this will assist our interpretation of findings. The process evaluation will combine quantitative data

(information on voucher use, household surveys) and qualitative data (interviews with vendors and information from 'mystery' shopper interviews with households and local stakeholders and community narratives).

Theoretical framework

The 2008 MRC framework emphasises the need for a strong theoretical foundation to inform evaluation. The study will be informed by Normalisation Process Theory (NPT) – a middle-range socio-behavioural theory (May & Finch, 2009) which has been most commonly used to assist understanding of interventions as part of feasibility studies and process evaluation (May et al., 2018). NPT offers a framework with 4 constructs and 16 sub-constructs to assess the behaviour change and work that individuals and groups do to implement new practices into their daily routine (e.g. eating more FV) (Finch et al., 2013). We will also incorporate Sekhon's framework (2017) in order to further our understanding the acceptability of the intervention.

The theoretical components of the process evaluation are reported in Table 5.

	Normalisation Pro	ocess Theory							
Construct	Households	FV vendors	Stakeholders						
Coherence The work of making sense individually and collectively about what the voucher scheme is and why it is important	Understanding the value of eating FV and how the voucher scheme works	Understanding how the voucher scheme works	Understanding how to adapt the food environment						
Cognitive Participation The work of building a community of practice around the voucher scheme	Engaging as a household/street /community in using vouchers	Engaging as a vendor and part of a supply chain in the increased provision of FV	Engaging with other stakeholders in the local area around the issue of FV uptake						
Collective Action The work of operationalising the voucher scheme	Use of the vouchers	Acceptance of the vouchers	Active support for the delivery of the voucher scheme in the wider local context						
Reflexive Monitoring The work of understanding how the voucher scheme affects the local FV environment.	How the voucher scheme changed FV consumption	How local FV supply chain was changed	How voucher scheme is understood to impact on local food system						

Table 5: Process Evaluation elements

We will be gathering intelligence throughout the pilot trial in order to understand the factors that may impact on the success or otherwise of the Fresh Street intervention. We have list some such factors that may impact on the success of the intervention below:

- Individual/ household level factors:
- Individual motivational level factors that contribute to purchasing and consuming FV
- Preference for shopping in supermarkets
- Use of other voucher schemes such as 'Healthy Start' and Rose vouchers.
- Lack of cooking skills, cooking resources (e.g. access to gas/electricity, cooker)
- Stigma associated with using the vouchers within retail outlets

Societal/ community level factors:

- Availability of preferred and/or culturally appropriate FV within the retail outlets taking part
- National or local media campaigns (e.g. Marcus Rashford and free school meals).
- National and/or local lockdowns relating to COVID-19 which impact access to local shops
- Prices of food and costs of living in relation to the voucher value
- Promotions on fruit and vegetables in supermarkets
- Change in prices in participating and not-participating FV retailers
- Project/ research specific factors:
- Availability of funding to cover the costs of the vouchers within study areas
- Challenges in terms of weekly distribution and reimbursement of vouchers
- Willingness of households to use the Fresh Street vouchers and/or complete survey materials needed to gather information on the schemes impact
- Number of local fruit and vegetable retailers willing to engage in the project

8. Ethics and Research Governance

The study will be sponsored by QMUL and will be managed by this institution in collaboration with the University of Sheffield and the University of Cambridge.

8.1. Ethical issues

We seek Queen Mary University of London Research Ethics Committee approval for the pilot study (we will submit a second application for the main trial).

Approval for additional NHS components for the pilot (i.e. the use of NHS staff to deliver the intervention and support the evaluation) will be sought from the NHS via the Health Research Authority (HRA).

The study will be carried out according to the principles of the Helsinki Agreement and in line with Good Clinical Practice.

This is a low-risk intervention. However, we will be alert to any possible unintended consequences of the intervention, and if we come across a safeguarding issue we will alert the relevant authorities.

A number of ethical issues regarding the **design of the intervention** have already been addressed in the earlier MRC funded Fresh Street development and feasibility study (Relton et al, 2020). For example, the vouchers are **only** exchangeable with local (non-supermarket) suppliers of fresh fruit and veg, thus reducing the risk that vouchers are exchanged for cigarettes/ alcohol, and the vouchers are available to **all** households regardless of income or size of household – thus **avoiding stigma** that is often associated with voucher schemes.

With regards to the **evaluation** there are substantial long standing barriers to public participation in health research (lack of saliency, lack of trust, and concerns relating to lack of privacy and agency) particularly from those groups characterised as 'hard to reach' – many of whom live in areas of high deprivation. This is an ethical challenge for those designing and conducting research. To address this challenge we have sought to minimise the amount of personal information requested and enabled paper and online surveys to be completed with just the name of the street, house number and area provided (See Section 7.9 for details as to what information we seek to collect from individuals.)

Participants may withdraw at any time, up to the point of data analysis when data will be aggregated. Participants will be able to withdraw without giving any reason. Data collected up to the point of withdrawal will be retained for analysis. For interviews, to compensate householders in the intervention and control areas who complete paper surveys and/or agree to take part in qualitative interviews (5-15 minutes in duration) we will offer each householder one £5 local shop voucher.

If online surveys are used and there is insufficient response then we will offer incentives in the form of a Prize drawer entry for £20 voucher for each completed valid online survey.

8.2. Data protection

Survey and interview respondents will be allocated unique study ID numbers. We will manage data and its protection according to principles of good research practice, Data Protection Act (DPA) 2018, GDPR, the Research Governance Framework for Health and Social Care (UK) and in line with PCTU Clinical Trials Unit protocols.

8.3 Record retention and archiving

The UK Policy Framework for Health and Social Care Research requires that research records are kept for 5 years after the study has completed. For studies sponsored by Queen Mary the approved repository for long-term storage of local records is the Trust Corporate Records Centre. All research documentation must be archived in physical form; electronic archiving is not accepted. This section should explain the arrangements for archiving study documentation after the study has ended, and the final destruction of the records.

9. Public involvement

To ensure outputs achieved meet the needs of user and beneficiaries, we will engage stakeholders through a wide range of activities with both direct and indirect beneficiaries.

Direct beneficiaries include: households in the intervention areas, local independent fresh FV retailers, Public health partners and local authority directorates in Bradford, Doncaster and Tower Hamlets.

Indirect beneficiaries include: Public Health England, Department of Health, Department of Communities, DEFRA, DWP, House of Lords Select Committee on Food, Poverty, Health and the Environment, House of Lords Regenerating Seaside Towns committee. House of Commons Committees: Environment, Food and Rural Affairs, Health and Social Care, Housing & Communities and Local Government. National and regional charities and food partnerships concerned with food access, food supply, and food security (Food Foundation, Sustainable Food Cities, NCVO, Church Action for Poverty, and Feeding Britain). In order to engage with both local and national stakeholders we have an outward facing website for the study, and will have social media (twitter) dissemination.

Local members of the public in Doncaster and Tower Hamlets continue to be actively involved including refining the methods used to collect information from households (paper and online surveys). Local members of the public will also help with the interpretation of the data and disseminating the findings.

Key Stakeholder meetings

We will hold meetings with local public health stakeholders at the start of the study in order to ensure our actions and methods are aligned and targeted. We will provide regular feedback reports on study progress and a concluding meeting to provide results and discuss strategies for moving forward. This engagement will enable greater understanding of FV uptake; greater understanding of local food insecurity in their areas, better tools for addressing food related health inequalities and food insecurity, and enable local decision makers to make interventions that are cost effective and evidenced based and that are located in local objectives. The study will provide understanding of place based voucher schemes and their potential links for strategic infrastructure development and planning guidance.

10. Safety considerations and reporting

This is a low-risk study.

Urgent Safety Measures

The CI may take urgent safety measures to ensure the safety and protection of the study subjects from any immediate hazard to their health and safety including COVID. The measures should be taken immediately. In this instance, the approval of the REC prior to implementing these safety measures is not required. However, it is the responsibility of the CI to inform the sponsor and Main Research Ethics Committee (via telephone) of this event immediately.

The CI has an obligation to inform both the Main REC in writing within 3 days, in the form of a substantial amendment. The sponsor (Joint Research Management Office [JRMO]) must be sent a copy of the correspondence with regards to this matter.

Annual Safety Reporting

The CI will send an Annual Progress Report to the QMUL REC using the NRES template and to the sponsor.

Overview of the Safety Reporting responsibilities

The CI has the overall oversight responsibility. The CI has a duty to ensure that safety monitoring and reporting is conducted in accordance with the sponsor's requirements.

11. Monitoring and auditing

The Sponsor or delegate retains the right to audit any study, study site or central facility. In addition, any part of the study may be audited by the funders where applicable.

The study will be audited by the PCTU Quality Assurance (QA) team in line with the Unit's internal Standard Operating Procedures.

In addition, the CI will provide six-monthly study reports to the IPSC, who act to monitor the study on behalf of the funder and sponsor.

12. Study committees

12.2. Patient and Public Involvement (PPI)

There will be extensive public engagement during the project. The PPI Group will help ensure that the perspectives and welfare of the public remain at the centre of the study throughout. The PPI group will provide comment and advice on study materials, support recruitment and retention in the study, and advise on dissemination of progress and findings.

12.3. Study Management Group (SMG)

The SMG is led by the study CI and comprises the study applicants, the Project Manager, and relevant members of the PCTU. Its role is to oversee the study delivery and progress, ensuring it is conducted in an ethical and competent manner, that it keeps to time, and delivers its planned outcomes. The PM reports to the PPI group to ensure the latter are appraised on study progress. PPI group members will be invited to join SMG meetings as required. The SMG will meet initially monthly and then at least every two months.

As there are no major safety issues and no foreseeable reason to stop the pilot trial for inefficacy, no Data Management Executive Committee (DMEC) is required.

13. Finance and funding

The **research costs** for the study are fully funded by the NIHR (Public Health Research) programme (NIHR129937).

Intervention costs: These costs are currently estimated to be £402,584.

We currently (11.4.21) have commitments to cover £202,283 (50%) of these estimated costs from three local councils:

- Bradford £15,000 (pilot) + £120,000 (main trial)
- Doncaster £26,000 (pilot)
- Tower Hamlets £15,283 (pilot)

This means that **all the intervention costs for the pilot** have been received

Additional sources of intervention costs

During the pilot we will seek to obtain additional intervention funding required for the main trial (objective i). Both Doncaster and Tower Hamlets councils have said that additional funding will be forthcoming if the pilots are viewed as 'successful'. However, no definitions of 'success' have been given and no amounts have been agreed.

We will also apply for Excess Treatment Costs (ETCs) from the Department of Health and Social Care (DHSC) subvention fund via PHE and also seek additional funds from corporate social responsibility funding sources.

14. Insurance and indemnity

The study sponsor is QMUL. The insurance that Queen Mary has in place provides cover for the design and management of the study as well as "No Fault Compensation" for participants, which provides an indemnity to participants for negligent and non-negligent harm.

15. Dissemination of findings

Our strategy is maximise public and professional awareness of the study and its relevance to public health nutrition policy. We have identified key stakeholder groups and linked these to our multi-channel approaches to influencing them. Dissemination is a standing item on the SMG agenda, ensuring interim study findings are rapidly and effectively communicated. Our PPI group will co-write or review all study outputs for dissemination via traditional and social media throughout the study.

The main outputs from the study will be a manual describing a potential new public health intervention (Fresh Street) and pilot trial data on the acceptability and effectiveness of this intervention that will be used to shape or influence local and national government policy relating to food systems, food insecurity, dietary quality and health inequalities.

This research has the potential to impact local communities (target streets) and those associated with services to these communities. The research will enable charities, third sector organisations, local authority public health and social exclusion teams as well as national government to acquire greater understanding of the ways to address poverty-associated issues of diet related public health. The research will have an impact in healthcare disciplines, public health nutrition, healthy eating programmes, health related behaviour change, healthy food systems and sustainable food economies. Beyond these, the research speaks to current debates in food poverty related research being studied by sociologists, anthropologists, economists, political scientists, psychologists, urban planners and geographers, and climate and environmental change. We anticipate media interest at a

local and national level due to the innovative nature of the intervention. We will also produce a policy briefing to be disseminated through local authority public health network.

16. Study Timetable

YEAR				2021												202	2					
Month	Oct	Nov	Dec	Jan	Feb	Mar	Apr	May	Jun	Jul	Aug	Sep	Oct	Nov	Dec	Jan	Feb	Mar	Apr	May	Jun	Jul
Project month number	1	2	3	4	5	6	7	8	9	10	11	12	13	14	15	16	17	18	19	20	21	2
NIHR funding																	EXT	EXT	EXT	EXT	EXT	EX
PROJECT SET UP AND DEVELOPMENT																						
Ethics committee review (QMUL) - non NHS																						
Ethics committee review - NHS																						
Protocol review - NIHR PHR & PSC																						
PILOT - non NHS sites																						
Randomise clusters																						
Intervention delivery																						
Baseline & 4 month* data collection - paper surveys																						
Baseline & 4 month* data collection - online surveys																						
Data collection - interviews																						
Process evaluation																						
PILOT - NHS site																						
Randomise clusters																						
Intervention delivery																						
Baseline & 4 month* data collection - paper/online survey	5																					
Data collection - interviews																						
Process evaluation																						
Pilot data analysis																						
Seek additional intervention funding for main trial																						
Progression criteria review - NIHR & PSC																						
*Decide if 4 month data collection required																						
Write up final report OR proceed to main trial																						
NIHR reports																						

17. References

Curtis, L.A. and A. Burns (2018). Unit Costs of Health and Social Care 2018. DOI: https://doi.org/10.22024/UniKent/01.02.70995.

Department of Health (2005) Choosing a Better Diet: a Food and Health Action Plan http://webarchive.nationalarchives.gov.uk/+/www.dh.gov.uk/en/publicationsandstatistics/publications/publicationspublications/publi

Department of Health (2019). Healthy Start Voucher Take-up. NHS. https://www.healthystart.nhs.uk/healthy-start-uptake-data/. Accessed November 2019

Department of Work and Pensions (2019): DWP launches national measurement of household food insecurity press release. https://foodfoundation.org.uk/wp-content/uploads/2019/04/National-measurement-of-food-insecurity-release.pdf

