6.3. Progression criteria

The following progression criteria will be assessed towards the end of the pilot study by and the NIHR and the independent project steering committee (PSC). They will consider the process data and decide whether it is feasible to proceed to a main trial. In order to evaluate the trial feasibility, the PSC will apply the following stop/ modify/ go progression criteria:

Green (continue):

- Demonstrated we can collect data on the primary outcome measure (i.e. >50% of both groups provide baseline data*)
- Secured intervention funding for at least 856 households for at least two years

Amber (decision required from funder on whether to continue to the main trial):

- Demonstrated we can collect data on the primary outcome measure (i.e. > 25% of both groups provide baseline data*)
- Secured intervention funding for at least 856 households for at least one year

Red (stop as not feasible):

- Not demonstrated we can collect data on the primary outcome measure (i.e. < 25% of both groups provide baseline data*)
- Not secured intervention funding for 856 households for at least one year

 * 50% of households in study streets provide information from at least one person in that household

7. Methods

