7.5. Sample size

Sample size for the pilot trial

The target for the pilot trial is 22 clusters (~300 households in each arm). - this is 33% of our main trial size and we think this is sufficient to enable us to address the objectives of the pilot.

There is no data from randomised trials that have used the portions of FV eaten yesterday questions on which to base a sample size calculation.

The original sample size calculation for the main trial (68 clusters with an estimated 856 households in each arm) was based on an increase of 0.5 in the number of portions of fruit and vegetables per person per day assuming a standard deviation of 2.0 (estimated for Health Survey for England 2017 taking into account our target population). This constitutes a small standardised effect size of 0.25. Stakeholder views of what constitutes a relevant increase in portions of FV eaten will be obtained during the pilot stage. Combining these with baseline cohort estimates of variability of portions of FV eaten will allow to assess whether effect size 0.25 will need to be revised and the required sample size be recalculated, changing the recruitment target for the main trial.

Sample size for process evaluation interviews

Semi-structured interviews (phone or face to face) will be conducted with up to 15 intervention households and up to 6 control householders or until data-saturation is reached. A purposive sampling strategy will then be adopted to ensure a full range of views, typical of the wider population. Maximum variation samples will be attempted based on (as far as possible): households who joined the Fresh Street scheme, households who dropped out of the scheme, and those with different ages, genders and ethnicities. All vendors will be contacted and invited to take part in interviews 3-4 months after the start of the intervention delivery.

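### Section 6.3 fixes the funding criterion at 856 households, although Section 7.5 allows the pilot to change that number; separately, the Section 13 funding total is £26,000 higher than its own list

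*Protocol*

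**What the plan says.** **Progression rule (protocol, Section 6.3).** The funding half of the rule is set in households and years. Green requires "Secured intervention funding for at least 856 households for at least two years". Amber requires "Secured intervention funding for at least 856 households for at least one year". Red applies if one year's money for those 856 households has not been obtained.

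**Where 856 comes from (protocol, Section 7.5).** It is the estimated number of households per arm in the original main-trial calculation, which used a difference of 0.5 portions and an SD of 2.0 (standardised effect 0.25). Stakeholders' opinion on a worthwhile difference and the spread of intake at baseline will then be used to judge whether 0.25 should be revised and "the required sample size be recalculated, changing the recruitment target for the main trial".

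**Funding position (protocol, Section 13).** On intervention costs: "These costs are currently estimated to be £402,584". As of 11 April 2021 the team reports that they "have commitments to cover £202,283 (50%) of these estimated costs from three local councils". The list below that statement reads "Bradford £15,000 (pilot) + £120,000 (main trial"), "Doncaster £26,000 (pilot") and "Tower Hamlets £15,283 (pilot").

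**The concern.** Two statements about the same number do not fit together. Section 7.5 treats 856 as provisional and names the pilot information that could change it. Section 6.3 treats it as fixed, in a rule applied towards the end of the same pilot, when that information will be at hand.

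The decision to proceed is at stake. If the reassessed size is above 856, Green can be met with money for a trial smaller than the one then known to be needed. If it is below 856, the rule can return Amber or Red for lack of money that the trial does not need.

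The Section 13 total is a separate and smaller matter. It does not agree with the amounts listed beneath it, so a reader gets too favourable a picture of funding at that date.

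**Working it through.** **1. What 856 contains.** Inputs from Section 7.5: difference δ = 0.5, SD = 2.0. The protocol does not state alpha or power for this calculation, so I assume two-sided 5% and show both usual powers.

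Unclustered n per arm = 2 × (z₁₋α/₂ + z₁₋β)² × (SD/δ)²

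- 80% power: 2 × (1.960 + 0.842)² × 16 gives 252; 856/252 = 3.4
- 90% power: 2 × (1.960 + 1.282)² × 16 gives 337; 856/337 = 2.5

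The 856 therefore includes an inflation of about 2.5 to 3.4 for clustering, non-response or both. Its components are not given, so 856 can be neither confirmed nor called wrong.

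**2. How far 856 would move.** Hold that inflation fixed and change only the two quantities that Section 7.5 says will be looked at. The new per-arm number is 856 × n(new)/337, using the 90% power figures rounded up to whole households. The ratio hardly depends on the power chosen. The alternative SDs and differences are illustrations, not forecasts.

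| δ | SD | Unclustered n per arm | Households per arm | 856 as share of need |
|---|---|---|---|---|
| 0.5 | 2.0 | 337 | 856 | 100% |
| 0.5 | 1.8 | 273 | 693 | 124% |
| 0.5 | 2.2 | 407 | 1,034 | 83% |
| 0.4 | 2.0 | 526 | 1,336 | 64% |
| 0.6 | 2.0 | 234 | 594 | 144% |

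A 10% change in the SD moves the requirement by about a fifth. A change of 0.1 in the worthwhile difference moves it by roughly a third downwards or more than a half upwards.

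**3. The Section 13 sum.**

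- Listed: £15,000 + £120,000 + £26,000 + £15,283 = £176,283
- Share of the estimate: 176,283/402,584 = 43.8%
- Stated: £202,283; 202,283/402,584 = 50.2%, so the printed 50% follows from the stated total
- Difference: £202,283 − £176,283 = £26,000

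No subset of the four amounts gives £202,283. It is obtained if the Doncaster £26,000 is counted twice, though the document does not say that this happened. Of the listed money, £56,283 is marked for the pilot and £120,000 for the main trial.

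**The case against.** The best defence of Section 6.3 is that it leaves room for judgement. The Green and Amber figures are minimums, the funder and steering committee weigh the process data before deciding, and Amber refers the decision to the funder. Recalculation is also conditional: Section 7.5 says the team will assess whether revision is needed. The main study has been removed from this version and needs its own ethics application, so its final size will be set elsewhere. This stands, and it lowers the chance of a wrong decision. It does not repair the rule. A minimum of 856 is still the wrong minimum if the requirement rises, and Red is written as a stop.

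A reader might infer that the go/no-go rule rests on the £202,283. The documents do not support that. Section 6.3 names no sum and does not cite Section 13. The total is a dated snapshot, the criteria are applied towards the end of the pilot, and raising more money in the meantime is objective i. Nor do the figures show the pilot to be underfunded: Section 13 says its intervention costs have all been received.

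The shortfall of £402,584 − £176,283 = £226,301 should not be read as the gap to Green or Amber either, because the protocol does not tie £402,584 to 856 households over one or two years.

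**Conclusion.** The inconsistency between Sections 6.3 and 7.5 holds and bears on the progression decision. It matters only if the reassessment changes the target. In that case, modest changes in the SD or the worthwhile difference move the per-arm requirement to anywhere from about 594 to 1,336 households against a fixed 856. Those figures assume that the unstated inflation for clustering and response stays as it was, and that alpha and power are conventional.

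A reader might go further and conclude that 856 is already too small or too large. That cannot be shown. The intracluster correlation (ICC), response rate and power behind it are not given, and plausible values for them give answers on both sides of 856.

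The Section 13 total is wrong against its own list by £26,000, which is 6.5% of the estimated cost. This is an administrative error, and correcting it moves no progression threshold.

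**What to change.** In Section 6.3, replace '856 households' in all three bands with 'the intervention-arm households required by the main-trial sample size as reassessed under 7.5 (856 if unchanged)'.

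In Section 7.5, add that the reassessment also uses the pilot's street-level ICC with its interval, and the baseline response rate. Streets are the unit of randomisation and Section 7.14 allows for correlation within them, so both affect the required number. Two limits should be stated. An ICC from 22 streets will be imprecise. Follow-up response will not be observed if the main trial goes ahead, because Section 7.11 says outcome data are then not collected in the pilot.

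In Section 13, correct the total to £176,283 (44%), or list the missing £26,000 commitment.

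The cost is a few lines of protocol text and one mixed model on the baseline data the pilot already plans to collect. The small downside is that the funding target is not final until the reassessment is done, so it should be completed before the progression review.
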